10.4 Severity (Intensity) of Adverse Event

The severity (intensity) of an adverse event will be rated on a three-point scale: (1) mild, (2) moderate, or (3) severe. It is emphasized that the term severe is a measure of intensity: thus, a severe adverse event is not necessarily serious. For example, itching for several days may be rated as severe, but may not be clinically serious.

-
- MILD: Usually transient, requires no special treatment, and does not interfere with the participant's daily activities.
 - MODERATE: Usually causes a low level of inconvenience or concern to the participant and may interfere with daily activities but is usually ameliorated by simple therapeutic measures.
 - SEVERE: Interrupts a participant's usual daily activities and generally requires systemic drug therapy or other treatment.

10.5 Expectedness

For a serious adverse event that is considered possibly related to study device, the Study Physician will classify the event as unexpected if the nature, severity, or frequency of the event is not consistent with the risk information previously described in the approved labelling of the study system.

10.6 Outcome of Adverse Events

The outcome of each reportable adverse event will be classified by the investigator as follows:

- RECOVERED/RESOLVED WITH NO SEQUELAE – The participant recovered from the AE/SAE without sequelae. Record the AE/SAE stop date.
- RECOVERED/RESOLVED WITH SEQUELAE – The event persisted and stabilized without change in the event anticipated. Record the AE/SAE stop date.
- FATAL – A fatal outcome is defined as the SAE that resulted in death. Only the event that was the cause of death should be reported as fatal. AEs/SAEs that were ongoing at the time of death; however, were not the cause of death, will be recorded as “resolved” at the time of death.
- NOT RECOVERED/NOT RESOLVED (ONGOING) – An ongoing AE/SAE is defined as the event was ongoing with an undetermined outcome. An ongoing outcome will require follow-up by the site in order to determine the final outcome of the AE/SAE. The outcome of an ongoing event at the time of death that was not the cause of death, will be updated and recorded as “resolved” with the date of death recorded as the stop date.
- ONGOING (MEDICALLY STABLE) – AE/SAE is ongoing, but medically stable. For example, a chronic condition where no further change is expected.
- UNKNOWN – An unknown outcome is defined as an inability to access the participant or the participant's records to determine the outcome (for example, a participant that was lost to follow-up).

If any reported adverse events are ongoing when a participant completes the study (or withdraws), adverse events classified as UADEs or related SAEs will be followed until they are either resolved, or have no prospect of improvement or change, even after the participant has completed all applicable study visits/contacts. For all other adverse events, data collection will end at the time the participant completes the study, unless further follow up is requested by the Study Physician. Note: participants should continue to receive appropriate medical care for an adverse event after their participation in the study ends.

If a participant is lost to follow up and participant outcome cannot be determined, outcome classification will be the last known outcome.

10.7 Reportable Device Issues

All UADEs, ADEs, device complaints, and device malfunctions will be reported irrespective of whether an adverse event occurred, except in the following circumstances.

The following device issues are anticipated and will not be reported but will report as an Adverse Event if the criteria for AE reporting described above are met:

- Component disconnections
- CGM sensors lasting fewer than the number of days expected per CGM labeling
- CGM tape adherence issues
- Pump infusion set occlusion not leading to ketosis
- Battery lifespan deficiency due to inadequate charging or extensive wireless communication
- Intermittent device component disconnections/communication failures not leading to system replacement
- Device issues clearly addressed in the user guide manual that do not require additional troubleshooting
- Skin reactions from CGM sensor placement or pump infusion set placement that do not meet criteria for AE reporting

10.8 Timing of Event Reporting

- UADEs must be reported within 10 working days to the FDA after the sponsor first receives notice of the adverse effect.
- Other reportable adverse events, device malfunctions (with or without an adverse event) and device complaints should be reported promptly, but there is no formal required reporting period.
- The IDE Sponsor will investigate the UADE and if indicated, report the results of the investigation to the IRBs and FDA within 10 working days of the study team becoming aware of the UADE per 21CFR 812.46(b) (2).
- The Study Physician will determine if the UADE presents an unreasonable risk to participants. If so, the Study Physician must ensure that all investigations, or parts of investigations presenting that risk, are terminated as soon as possible but no later than 5 working days after the Study Physician makes this determination and no later than 15 working days after first receipt notice of the UADE.
- In the case of a device system component malfunction (e.g. pump, CGM, control algorithm), information will be forwarded to the responsible manufacturer by the study personnel.

10.9 Stopping Criteria

10.9.1 Participant Discontinuation

A participant will be discontinued if any of the following occur:

- The Study Physician believes it is unsafe for the participant to continue the intervention. This could be due to the development of a new medical condition or worsening of an

-
- 1105 existing condition; or participant behavior contrary to the indications for use of the device
1106 that imposes on the participant's safety
- 1107 • The participant requests that the treatment be stopped
 - 1108 • Two distinct episodes of DKA
 - 1109 • Two distinct severe hypoglycemia events as defined in section 10.2.1.
 - 1110 • Two events of any kind: severe hypoglycemia or DKA

1111 **10.9.2 Suspending/Stopping Overall Study**

1112 In the case of an unanticipated system malfunction resulting in a severe hypoglycemia or severe
1113 hyperglycemia event (as defined in section 10.2.2), use of the study device system will be
1114 suspended while the problem is diagnosed.

1115 In the event that two distinct episodes of DKA or two distinct severe hypoglycemia events as
1116 defined in section 10.2.1 occur, the overall study would be suspended while the underlying
1117 conditions are determined.

1118 In addition, study activities could be similarly suspended if the manufacturer of any constituent
1119 study device requires stoppage of device use for safety reasons (e.g., product recall). The affected
1120 study activities may resume if the underlying problem can be corrected by a protocol or system
1121 modification that will not invalidate the results obtained prior to suspension. As previously noted,
1122 the Study Physician will review all adverse events and adverse device events that are reported
1123 during the study. The Study Physician may request suspension of study activities or stoppage of
1124 the study if deemed necessary based on the totality of safety data available.

1125 **10.10 Definition of a Data Breach**

1126 A data breach is defined in the HITECH Act (43 USC 17932) as an unauthorized acquisition,
1127 access, or use of protected health information (PHI) that compromises the security or privacy of
1128 such information.

1129 **Chapter 11: Miscellaneous Considerations**

1130 **11.1 Prohibited Medications, Treatments, and Procedures**

1131 Participants using glulisine at the time of enrollment will be asked to contact their personal
1132 physician to change their prescribed personal insulin to lispro or aspart for the duration of the trial.

1133 The study devices (study insulin pump, study CGM) must be removed before Magnetic Resonance
1134 Imaging (MRI), Computed Tomography (CT) or diathermy treatment. Participants may continue
1135 in the trial after temporarily discontinuing use if requiring one of the treatments above.

1136 **11.2 Participant Withdrawal**

1137 Participation in the study is voluntary. Participant may withdraw at any time. For participants who
1138 do withdraw from the study, the study team will determine if their data will be used in analysis.

1139 **11.3 Confidentiality**

1140 For security and confidentiality purposes, subjects will be assigned an identifier that will be used
1141 instead of their name. Protected health information gathered for this study may be shared with the
1142 third-party collaborators. De-identified subject information may also be provided to collaborators
1143 involved in the study after the appropriate research agreement has been executed.

1144 **11.4 Lost to Follow Up**

1145 If a participant is lost to follow up and participant outcome cannot be determined, outcome
1146 classification will be the last known outcome/contact with the participant. A participant will be
1147 considered lost to follow-up after three attempted contacts that do not result in any communication
1148 from the participant. A certified letter may be sent as the fourth and final attempt to communicate
1149 with the participant.

Chapter 12: Statistical Consideration

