6.6.1 Hypoglycemia

- a. If CGM falls below 70 mg/dL at any time, confirm <70mg/dL CGM readings and potential hypoglycemia symptoms with a fingerstick blood glucose. If blood glucose confirms <70mg/dL CGM reading, hypoglycemia will be treated with oral glucose of approximately 5-15 g. Participants will be encouraged to wait 15 min prior to giving a second glucose treatment. These fingerstick checks will be performed during the hotel stay and during the home portion if the participant chooses to do so. During the hotel stay we will also recheck a fingerstick blood glucose before retreatment.
- b. If a participant experiences any symptoms of hypoglycemia (e.g., shakiness, dizziness, sweating, pallor, clumsiness, difficulty paying attention, or tingling around the mouth), then the participant should treat with oral glucose of 5-15 g. Participants will be encouraged to wait 15 min prior to giving a second glucose treatment. During the hotel portion of the study, a fingerstick blood glucose will be assessed before such treatment for symptoms and before any re-treatment.
- c. If a participant displays any signs of neuroglycopenia (e.g., lethargy, disorientation, confusion, or inappropriate behavior) or severe hypoglycemia (e.g., hypoglycemic seizure, loss of consciousness, inability to properly consume treatment)

hypoglycemia will be treated with either oral glucose or glucagon. The patient will be discharged from the study. The participant should consult with study physician to discuss next steps for broader evaluation of symptoms unrelated to hypoglycemia.

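### Section 10.9.2 does not require a study pause after one severe hypoglycaemia and one DKA, although 10.9.1 pools the two types for an individual

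*Combined protocol and SAP*

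**What the plan says.** **Study level (10.9.2).** The count rule begins "In the event that two distinct episodes of DKA or two distinct severe hypoglycemia events as" defined in 10.2.1; if either count is reached, the study is suspended while the causes are examined. There is no clause for one event of each type.

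**Participant level (10.9.1).** The list has two DKA episodes, two severe hypoglycaemia events, and then a third, pooled entry: "Two events of any kind: severe hypoglycemia or DKA".

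**Other routes to a study-level pause.**
- Malfunction (10.9.2): "In the case of an unanticipated system malfunction resulting in a severe hypoglycemia or severe" hyperglycaemia event, use of the device system is suspended. One event is enough, but it must result from an unanticipated malfunction.
- Discretion (10.9.2): "The Study Physician may request suspension of study activities or stoppage of" the study, on the totality of the safety data.
- Unanticipated adverse device effect, UADE (10.8): if the Study Physician finds an unreasonable risk, the affected investigations must be "terminated as soon as possible but no later than 5 working days after the Study Physician makes this determination", with an outer limit of 15 working days from first notice.

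**Discharge after severe hypoglycaemia (6.6.1c).** For signs of neuroglycopenia or severe hypoglycaemia: "The patient will be discharged from the study".

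**Reporting time (10.8).** Reportable adverse events other than UADEs "should be reported promptly, but there is no formal required reporting period".

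**The concern.** The plan treats the mixed pair as a case of its own and closes it for the individual, but leaves it open for the study. A mandatory count exists so that a pause does not depend on judgement alone. Here, two of the most serious expected harms of automated dosing could occur in two people without meeting the count, while other participants go on using a new bolus-priming module, some of them at home. Safety is a stated objective of this pilot, so the rule that protects it should not turn on whether the second event has the same name as the first.

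**Working it through.** **1. Which event histories trigger a mandatory pause?** (SH = severe hypoglycaemia; no malfunction or UADE route assumed.)

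| SH | DKA | 10.9.2 count | Any-two count |
|---|---|---|---|
| 2 | 0 | pause | pause |
| 0 | 2 | pause | pause |
| 1 | 1 | no mandatory pause | pause |
| any three events | | pause | pause |

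Any three events must include two of one type, so the current rule is met by the third event at the latest. The two rules differ only while the history is exactly one of each, and the difference is one event.

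**2. Does 10.9.1 fill the gap?** It counts within a person. Under 6.6.1c a participant leaves after a first severe hypoglycaemia, so a mixed pair in one person essentially requires the DKA to come first. If a site instead followed the two-event wording of 10.9.1 and kept such a participant in, the pooled entry would remove that person only. Under 10.9.2 the study would still not have to pause.

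**3. How conditional are the other routes?** Section 10.1.5 defines a malfunction as failure to meet specifications or to perform as intended; a dosing policy that runs as coded but doses poorly for some users may not qualify. A UADE must not have been identified beforehand in nature, severity or incidence (10.1.3). Section 9.1.4 already names fainting and seizures and 9.1.5 names hyperglycaemia and ketonaemia, so many trigger events may not be UADEs. What remains is discretion.

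**4. Size.** The plan states no operating characteristic for the rule, so there is none to reproduce, and it gives no event rates. Assumptions: each participant has at most one SH (risk *p*) and at most one DKA (risk *q*), all independent. N = 16 is the completion goal in 3.2.

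- P0 = (1−*p*)^N and P1 = N·*p*·(1−*p*)^(N−1); likewise for DKA with *q*.
- Two or more of one type: S = 1 − P0 − P1 for SH, and D likewise for DKA.
- Current rule: 1 − (1−S)(1−D).
- Exactly one of each (the gap): P1(SH) × P1(DKA).
- Any-two rule: current rule + gap.

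For *p* = *q* = 1%, N = 16:
- P0 = 0.99^16 = 0.8515; P1 = 16 × 0.01 × 0.99^15 = 0.1376; S = D = 0.0109.
- Current: 1 − (1 − 0.0109)² = 2.17%.
- Gap: 0.1376² = 1.89%.
- Any-two: 4.07%.

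| N | Risk of each event | Current | Any-two | Gap (points) |
|---|---|---|---|---|
| 16 | 0.5% | 0.57% | 1.12% | 0.55 |
| 16 | 1% | 2.17% | 4.07% | 1.89 |
| 24 | 0.5% | 1.28% | 2.42% | 1.14 |
| 24 | 1% | 4.71% | 8.34% | 3.63 |

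N = 24 is the enrolment ceiling in 3.2 and an upper bound, because not everyone enrolled will use the device. Independent Poisson totals give nearly the same result at N = 16 and 1% each: 2.3% to 4.2%.

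**5. Share of two-event histories missed.** If a fraction *s* of events are SH and types are independent, a first pair is mixed with probability 2*s*(1−*s*): 50% at *s* = 0.5, 32% at 0.8, 18% at 0.9 (assumed splits).

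**The case against.** **A within-type count can be defended.** Two events of one kind point to a common fault more strongly than one over-delivery and one under-delivery. A reader might infer from 9.1.11 that both harms share a single cause in automated dosing. The text does not support that: it ties hypoglycaemia to automated dosing and hyperglycaemia to automated attenuation, which are opposite mechanisms, and 9.1.5 adds pump and infusion-set failure. Also, 10.9.1 asks a different question, whether one person should go on. This stands as a reason why the authors might have chosen the rule. It is not a stated reason, and it does not show that the mixed pair is better left to discretion in a small pilot whose sponsor already pools the two types for an individual.

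**Other safeguards exist.** A reader might infer that the study would carry on unchecked after a mixed pair. It would not: the malfunction and UADE routes may apply, and the Study Physician reviews every reported event and can ask for a pause. The gap is only that the pause is not mandatory.

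**The higher risks are strained.** At 2% for each event the trigger would rise from 7.8% to 13.4% at N = 16. Over about 20 days of device use (Days 2 to 21 in Table 1), 2% is 0.02 × 365/20 = 0.37 events per person-year; even 0.5% is 0.09. Section 3.5 excludes people with DKA, or severe hypoglycaemia with seizure or loss of consciousness, in the past 12 months. The 2% figures should not be used to argue the point. The calculation also spans the whole study, including the first home week on unmodified AIDANET.

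**Reporting time.** A reader might infer from 10.8 that trigger events could go unnoticed for long. The documents do not support this. The section asks for prompt reporting, and the untimed bullet names no recipient. Hotel staffing and on-call cover (6.2), home CGM alerts (7.2), physician consultation under 6.6.1c ("The participant should consult with study physician to discuss next steps") and Study Physician review of each adverse event form (10.2.2) make early awareness likely. The study policies document cited in 9.2 was not available for this review and may set a limit.

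**Conclusion.** The point holds on the wording alone: one severe hypoglycaemia and one DKA do not trigger mandatory study suspension, the pair will mostly fall outside 10.9.1, and absent a qualifying malfunction or UADE the pause is discretionary. The size is small: about 0.6 percentage points at an assumed 0.5% risk of each event and about 1.9 at 1%, for 16 participants. These figures rest on assumed, independent risks, count only the mandatory trigger and give no credit to the other routes. The conclusion does not depend on them. This is a cheap improvement to a safety rule; it does not affect the analysis of the primary outcome. The missing notice time in 10.8 is a minor matter of detail and does not carry the point.

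**What to change.** In 10.9.2, replace the two within-type counts by one: suspend the overall study after any two events of severe hypoglycaemia or DKA across participants, with the definitions in 10.2.1 and 10.2.2. Leave the malfunction, UADE and discretionary routes as they are.

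The cost is protocol wording and, for a mixed pair, a pause at the second event instead of the third at the latest. At the assumed risks this nearly doubles a rare occurrence. The pause is not always free: both 18-hour periods run within one hotel stay, and 3.7 replaces dropouts only before hotel admission, so a pause during a stay could lose a crossover pair. That is an acceptable price in a study whose purpose is safety and feasibility.

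As a minor accompanying change, state in 10.8 an internal notice time to the Study Physician for these trigger events, for example 24 hours from awareness by any study staff, or cite the study policies document if it already sets one.

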12.1 Design and Randomization

This pilot study aims to demonstrate the safety and feasibility of the AIDANET+BPS_RL algorithm, which replaces with a new BPS_RL the bolus priming module of our AIDANET system described in IDE #G240236, which was approved by the FDA on October 10, 2024.

As presented in Figure 1, this study is a randomized cross-over trial comparing AIDANET to AIDANET+BPS_RL, which includes the new BPS_RL. A week of AIDANET control at home will be followed by a two-night hotel stay where participants will cross over from AIDANET to AIDANET+BPS_RL and vice versa and will learn how to operate the new BPS_RL for a subsequent AIDANET+BPS_RL week at home. The participants are not expected or encouraged to announce meals to the system, thus the system will run in fully-automated closed loop (FCL) mode.

Eligible participants will be randomized to two groups, A and B, which differ only by the order of administration of AIDANET or AIDANET+BPS_RL during the hotel section of the study. The remaining procedures are identical for both groups A and B. The randomization list will use a sequence of computer-generated pseudorandom Bernoulli trials and will aim to balance groups by baseline HbA1c (Figure 1).

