2.5 Timing of Device Use

Following screening and randomization, all participants will be trained on the use of the study equipment and AIDANET algorithm. Participants will be connected to a Dexcom G6 sensor and the Tandem t:AP pump, which will be connected to the DiAs platform. AIDANET will be started on DiAs, and the participants will be trained how to use the Dexcom G6 sensor (if using Dexcom G7 in their AID system), the Tandem t:AP pump, and DiAs/AIDANET (see Table 1 and Figure 1). The t:AP pump will be programmed with back up parameters determined by the study investigator(s). Once started, the participants will have their glucose values managed through use of this system during the At-Home and hotel periods.

One-Week AIDANET: All participants will collect approximately one week of AIDANET baseline data. During this period, participants will generally use AIDANET in FCL mode. The DiAs Remote Monitoring will be on, supervised by study personnel.

Hotel Session: Participants will arrive at the hotel in the afternoon (prior to dinner). Those randomized to Group A will continue to use their AIDANET system. Those randomized to Group B will be switched to the AIDANET+BPS_RL system. Because AIDANET and AIDANET+BPS_RL have identical user interfaces and only the priming bolus calculation is changed “under the hood,” no additional training will be needed.

One-Week AIDANET+ BPS_RL: Participants will continue to use the Tandem t:AP pump, DiAs platform running the AIDANET+ BPS_RL, and Dexcom G6 CGM for glucose control for 7 days/6

243 nights during this period. The DiAs Remote Monitoring will be on, supervised by study personnel.
244 At the end of this period participants will return to their usual diabetes therapy.

245 **2.6 Meal Testing**

246 During the home study, participants will be instructed to consume their usual diet and will not be
247 required to record the timing of the meals. 2.3

248 **2.7 Study Devices Download**

249 Data from the study devices will be captured in real-time by the remote monitoring server for the
250 DiAs system. In addition, study devices will be downloaded at the end of the home visits.

251 **2.8 Study System Issues**

252 If the CGM signal becomes unavailable for more than 20 minutes consecutively, closed loop will
253 not operate to automatically adjust insulin delivery. If the CGM is not connected, the system will
254 revert to the usual open loop function of the pump and deliver insulin with the pre-programmed

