386 If an exclusionary condition is identified, the study participant will be excluded from participation
387 with follow up and referral to their primary care physician as needed.

388 If the study participant is pregnant, the study physician will discuss the results of the blood test
389 with the participant and the participant will be asked to seek confirmation of the test and the
390 appropriate medical care.

391 Participants who screen-fail or dropout will be replaced if it occurs prior to the Hotel Admission.
392 Screen failed participants may be re-screened if their clinical situation changes as determined by
393 the study physician.

394 **3.8 Personal Equipment Downloads**

395 Up to 6 months of historical data from the participant's personal insulin pump, glucometer, or
396 continuous glucose monitor may be downloaded or recorded. Data will be obtained from the
397 participant's personal insulin pump, glucometer and CGM. This data may be obtained through the
398 commercial applications (e.g., Source, Tidepool, and Dexcom).

399 **3.9 Surveys**

400 Participants will be asked to complete the Demographic Data Survey, INSPIRE Survey, and
401 Technology Expectations Survey as described in section 8.2 prior to using AIDANET equipment.

402 **3.10 Other Considerations**

403 This study is not meant to find out if the participant has any other disease or problem. The study
404 leaders will alert the participant if any of the research results are important to the participant's
405 health during the study. The participant may have a copy of the screening tests to discuss with the
406 personal physician. If blood tests are completed, any blood left over will be thrown away. It will
407 not be stored for any future testing.

408 **3.11 Randomization**

409 Once eligibility is met and screening procedures are completed, the participant will proceed to
410 Randomization. Participants will be randomized 1:1 to one of two groups:

411 **GROUP A:** AIDANET followed by AIDANET+ BPS_RL during the hotel session

412 **GROUP B:** AIDANET+ BPS_RL followed by AIDANET during the hotel session

413 Randomization will occur via REDCap module.

Chapter 4: Study Devices & Training Visit

Visit 2

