An HbA1c value for the participant will be collected prior to the start of the DiAs system. This can be a point-of-care value, lab value, or historical value from within 4 weeks of signing consent. Participants will be asked to place a new sensor 24-72 hours prior to the start of the Visit 2 to allow time for the CGM to warm-up prior to DiAs initialization. The study system is designed to enable full closed loop control and consists of the following elements: the diabetes assistant (DiAs) prototyping platform (smart phone), connected to a Tandem t:AP research insulin pump and a Dexcom G6 CGM.

Participants will come to the research center for initiation and training on the study device as described in Section 4.1. This will consist of 4-8 hours of training, tailored to the individual and include a supervised meal/snack. The participant will be asked to have an active Dexcom G6 sensor by the start of Visit 2; otherwise, a new CGM sensor will be placed. The study team will perform vital signs and inquire about any changes to the participant's medical history. Any changes to medical history will be communicated to the medical physician to ensure continued eligibility and participation.

The participant's CGM reading, and ketone concentration will be recorded. In the event that the participant's CGM reading is not between 80-250 mg/dL or ketone concentration is ≥ 0.6 mmol/L prior to initiation of the FCL system, the study physician may recommend additional insulin dosing according to the participants' usual doses. Study physician may elect to cancel participant's participation in the study if concerned about their medical safety. This participant will not be replaced.

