8.1 Laboratory and Point of Care Testing

8.1.1 HbA1c

A blood sample (either capillary or venous draw) will be obtained at screening to obtain a baseline Hemoglobin A1c level. A blood test obtained within 4 weeks prior to enrollment may be used. HbA1c level may be measured by the study team using the DCA2000, a comparable point of care device, at time of screening. Labs may be obtained at a local laboratory (e.g., LabCorp, Quest) convenient to the participant.

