12.4 Planned Analysis

The primary statistical effect of interest is the change in TIR resulting from the transition from AIDANET to AIDANET+BPS_RL and vice versa. Thus, the analysis will involve use of repeated measures General Linear Model (GLM), with emphasis on the interaction corresponding to the crossover design. The analysis will use covariates, e.g., baseline HbA1c, gender, and TIR within the first week on AIDANET alone (see Figure 1).

All secondary outcomes will be similarly analyzed. In particular, the CGM-based metrics of the last 3 days on AIDANET will be compared to the last 3 days on AIDANET+BPS_RL using repeated measures CLM with covariates as described above. If the distribution of an outcome is not suited for GLM (e.g., profound skewness, or atom at boundary), we will perform paired Wilcoxon signed rank test (and lose the capacity to use covariates) to test difference in the median instead of the mean; this is expected for time < 54 mg/dl and possibly time >250 and 300 mg/dL.

We do not plan to correct for multiple comparisons. We do not expect substantial missing values in this supervised study, but if more than 20% of the data for the primary outcome is missing, we will consider switching to mixed models that handle missing data better.

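### Bernoulli draws neither fix the sequence split nor use HbA1c, and the documents disagree on whether HbA1c is on file when participants are randomised

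*Combined protocol and SAP*

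**What the plan says.** **Allocation.** Section 3.11: "Participants will be randomized 1:1 to one of two groups", the groups being the two orders of controller use in the hotel. On method it adds only: "Randomization will occur via REDCap module". Section 12.1 describes the list: "The randomization list will use a sequence of computer-generated pseudorandom Bernoulli trials and will aim to balance groups by baseline HbA1c". It gives no block size, HbA1c cut-point or minimisation rule.

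**Timing of allocation.** Section 3.11 sits in the Visit 1 chapter and begins: "Once eligibility is met and screening procedures are completed, the participant will proceed to" randomisation. Table 1 marks randomisation at Visit 1, and section 2.5 puts it before device training.

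**Timing of HbA1c.** Chapter 4 (Visit 2): "An HbA1c value for the participant will be collected prior to the start of the DiAs system". Section 8.1.1 says that a sample "will be obtained at screening to obtain a baseline Hemoglobin A1c level".

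**Analysis.** Section 12.4 plans a repeated-measures GLM centred on the crossover interaction, with baseline HbA1c among the covariates. For outcomes with unsuitable distributions, "we will perform paired Wilcoxon signed rank test (and lose the capacity to use covariates"). This is expected for time below 54 mg/dL and possibly for time above 250 and 300 mg/dL. Section 12.6 judges success on differences in TIR, TBR and TAR between the systems, TIR regardless of p-value, and does not say whether those differences are adjusted for period.

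**The concern.** In its standard meaning, a sequence of Bernoulli trials is simple randomisation: each draw ignores both earlier allocations and the participant's HbA1c. Section 12.1 therefore sets a balancing aim that its stated method cannot serve, and a programmer could not build the list from that sentence. If HbA1c is first recorded at Visit 2, as Table 1 shows, the balancing variable would also be missing when the sequence is drawn.

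In a two-period crossover, sequence balance keeps the difference between the first and second hotel session out of an unadjusted treatment comparison. With about 16 participants, marked imbalance is not rare. A period-adjusted analysis pays for it in precision. An analysis without a period term carries part of the period effect into the treatment estimate.

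**Working it through.** **Inputs.** Completers: 16 (protocol summary, sections 2.3 and 3.2). Section 12.2 has 15, with recruitment up to 20; section 3.2 enrols up to 24. Ratio: 1:1 (section 3.11). Draw probability: not stated, so 0.5 is assumed from the ratio. Period effect: not given, so it is kept as a symbol.

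**1. The stated ratio.** The expected size of each group is 16 × 0.5 = 8, so 1:1 is reproduced in expectation. The standard deviation of one group's size is √(16 × 0.25) = 2.

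**2. Realised split.** P(k) = C(16,k)/2^16, with 2^16 = 65,536.
- 8:8: 12,870/65,536 = 19.6%
- 7:9: 2 × 11,440/65,536 = 34.9%, so 7:9 or better is 54.5%
- 6:10: 2 × 8,008/65,536 = 24.4%
- 5:11 or worse: the remainder, 21.0%

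The other sizes in the plan change little. The chance of exact balance is 17.6% at 20 and 16.1% at 24; at 15, the chance of 7:8 is 39.3%.

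**3. Precision of a period-adjusted effect.** Its variance is proportional to 1/nA + 1/nB, which is 1/8 + 1/8 = 0.25 at 8:8.

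| Split | Variance ratio | SE ratio |
|---|---|---|
| 7:9 | (1/7 + 1/9)/0.25 = 1.016 | 1.008 |
| 6:10 | (1/6 + 1/10)/0.25 = 1.067 | 1.033 |
| 5:11 | (1/5 + 1/11)/0.25 = 1.164 | 1.079 |
| 4:12 | (1/4 + 1/12)/0.25 = 1.333 | 1.155 |

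**4. Shift in a period-blind comparison.** Let τ be the treatment effect (BPS_RL minus AIDANET) and π the effect of the second hotel session relative to the first. The within-participant difference has mean τ + π in Group A (AIDANET first) and τ − π in Group B. The raw paired mean therefore estimates τ + π(nA − nB)/N. At 5:11 the shift has size (6/16)π = 0.375π. Averaging the two sequence means instead gives [(τ + π) + (τ − π)]/2 = τ at any split. For scale, moving a raw TBR difference by the whole 3-point margin of section 12.6 at 5:11 would need a period effect of 3/0.375 = 8 percentage points.

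**5. HbA1c balance.** In 100,000 simulated trials of 16 with standardised normal HbA1c, the SD of the between-group difference was 0.52 SD under Bernoulli draws and 0.50 under one fixed 8:8 block. It was 0.32 with blocks of 2 within two HbA1c strata, which also gave 8:8 in 75% of trials and never worse than 7:9. Blocking alone fixes the split; the HbA1c aim needs strata.

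**6. When HbA1c is obtained.**

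| Place | Timing |
|---|---|
| Table 2 | Enrolment, Visit 1 |
| Section 8.1.1 | Screening; a value from the 4 weeks before enrolment is accepted |
| Section 3.6 | A value from the previous month may serve as the enrolment value; the screening labs list only a pregnancy test |
| Table 1 | Visit 2 |
| Chapter 4 | Before DiAs starts, at Visit 2; a historical value within 4 weeks of consent is accepted |

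The first three are compatible with a value in hand at Visit 1. The last two allow it to arrive after allocation.

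**The case against.** The strongest reply is that the plan promises little and risks little. A ratio of 1:1 is met in expectation, and section 12.1 only aims at balance. The sentence also cites Figure 1, which I have not seen and which may add detail. Most splits are harmless: 7:9 or better occurs in 55% of cases and costs at most 0.8% in standard error. The contrast is within participant, so a difference in HbA1c between sequences does not directly bias it, and HbA1c is a planned covariate. The GLM's crossover interaction separates treatment from period. The Wilcoxon fallback is expected only for secondary outcomes, the 0.375 factor is conditional on a 5:11 split, and over repeated fair randomisation the shift averages to zero.

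All of that stands as a limit on size. The method in the text still cannot serve the HbA1c aim, and the documents still conflict on timing. The trial will have one realised split, so averaging to zero over repetitions does not protect its result.

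A reader might infer that the 1:1 split and HbA1c balance cannot be achieved, or that HbA1c is unavailable at randomisation. The documents do not support either. Bernoulli draws at 0.5 respect the ratio in expectation, and several sections place or accept an HbA1c value at Visit 1, so a stratified REDCap list remains possible.

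**Conclusion.** The point holds as a modest design weakness together with an internal contradiction. Neither an equal split nor HbA1c balance is assured by the method in section 12.1, and the HbA1c timing must be reconciled with randomisation at Visit 1. Under simple randomisation with probability 0.5 and 16 participants, there is a 21% chance of a split at least as uneven as 5:11. At 5:11 the period-adjusted analysis loses 8% in standard error (16% in variance). Period-blind hotel comparisons shift by 0.375 times a period effect of unknown size. These are the signed-rank fallback and, if taken as raw means, the section 12.6 differences; for the signed-rank test the factor is a guide, since it is derived for means. Without a period effect there is no shift.

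The home comparison is outside this point: every participant uses AIDANET first there, so sequence balance has no bearing on it. Section 2.5 notes identical interfaces, from which a reader might infer a bias from early knowledge of the order. The documents do not say when participants learn their order, so no such conclusion is drawn.

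**What to change.** 1. **Allocation (section 12.1).** Replace the Bernoulli sentence with permuted-block 1:1 allocation, in small blocks within two HbA1c strata with a stated cut-point, implemented in the REDCap module.
2. **HbA1c timing.** Require an HbA1c value on file before allocation, and align Tables 1 and 2, sections 3.6 and 8.1.1, and Chapter 4. Drawing the sequence nearer the hotel stay is optional. Table 1 puts about 10 days between randomisation (Day 1) and the hotel (Day 11), and section 3.7 replaces participants lost before admission, so a later draw would limit disturbance of the split. Section 12.1 says that the groups differ only in hotel order, so nothing earlier depends on the allocation.
3. **Hotel analysis (sections 12.4 and 12.6).** For hotel outcomes not suited to the GLM, replace the paired signed-rank test with a rank-sum test comparing within-participant period differences between the two sequences, with a Hodges-Lehmann interval. The shift between sequences is (τ + π) − (−τ + π) = 2τ, so halve it. Take the hotel differences used for the success criteria from a period-adjusted estimate. Leave the home comparison as it is.

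The cost is protocol wording and a REDCap allocation table, with no added visits or participants.
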